6.4 Safety

6.4.1 Definition of adverse events

An adverse event is the development of an undesirable medical condition or the deterioration of a pre-existing medical condition following or during exposure to a pharmaceutical product, whether or not considered causally related to the product. An undesirable medical condition can be symptoms (e.g., nausea, chest pain), signs (e.g., tachycardia, enlarged liver) or the abnormal results of an investigation (e.g., laboratory findings, electrocardiogram). In clinical studies, an AE can include an undesirable medical condition occurring at any time, including run-in or washout periods, even if no study treatment has been administered.

The term AE is used to include both serious and non-serious AEs.

6.4.2 Definitions of serious adverse event

A serious adverse event is an AE occurring during any study phase (ie, run-in, treatment, wash-out, follow-up), that fulfils one or more of the following criteria:

- Results in death
- Is immediately life-threatening
- Requires in-patient hospitalization or prolongation of existing hospitalization
- Results in persistent or significant disability/incapacity or substantial disruption of the ability to conduct normal life functions
- Is a congenital abnormality or birth defect

- Is an important medical event that may jeopardize the subject or may require medical intervention to prevent one of the outcomes listed above.

The causality of SAEs (their relationship to all study treatment/procedures) will be assessed by the investigator(s) and communicated to AstraZeneca.

6.4.3 Recording of adverse events

Time period for collection of adverse events

All adverse events, serious or non-serious, are to be recorded on the Adverse Event Form, which accompanies the CRF. This should be done as soon as possible but no longer than 24 hours after the event. The Investigator should specify the date of onset, seriousness, intensity, action taken on the study drug/device, corrective therapies given, outcome, date of resolution (if any), and his/her opinion as to whether the AE can be related to therapies or procedures involved in the study. The Investigator should also review with the monitor the suggested categories used for describing the relationship(s).

Follow-up of unresolved adverse events

Subjects withdrawn from the study due to any AE that is still ongoing will be followed at least until the outcome is determined, even if it implies that follow-up continues after the subject has left the study, and where appropriate until the end of the planned period of follow-up.

In the case of an SAE that is still ongoing, the subject must be followed-up until clinical recovery is complete or until progression has been stabilized. It may imply that this follow-up will continue after the subject has left the study.

As obtained, additional information will be noted on follow-up "Serious Adverse Event" Forms. As these are completed, the box marked "follow-up" is to be checked on these forms and the forms sent or faxed to the Medical Monitor.

The Sponsor is responsible for reporting faxed SAEs within required timelines promptly to the Health Authorities of different countries, as appropriate, except in those countries where it is the Investigator's legal responsibility.

The following variables will be collected for each AE:

- AE (verbatim)
- The date and time when the AE started and stopped
- Maximum intensity, intensity, or changes in intensity of AE
- *Select the appropriate if needed: CTCAE grade/max CTAE grade/changes in CTCAE grade*
- Whether the AE is serious or not

- Investigator causality rating against the Investigational Product (yes or no)
- Action taken with regard to investigational product
- *Select the appropriate if needed:* AE caused subject's withdrawal from study (yes or no)
- Outcome.

In addition, the following variables will be collected for SAEs:

- Date AE met criteria for serious AE
- Date Investigator became aware of serious AE
- AE is serious due to
- Date of hospitalization
- Date of discharge
- Probable cause of death
- Date of death
- Autopsy performed
- Causality assessment in relation to Study procedure(s)
- Causality assessment in relation to Other medication
- Causality assessment in relation to Additional Study Drug
- Description of AE.

It is important to distinguish between serious and severe AEs. Severity is a measure of intensity whereas seriousness is defined by the criteria in Section 6.4.2. An AE of severe intensity need not necessarily be considered serious. For example, nausea that persists for several hours may be considered severe nausea, but not a SAE. On the other hand, a stroke that results in only a limited degree of disability may be considered a mild stroke but would be a SAE.

Adverse Events based on signs and symptoms

When collecting AEs, the recording of diagnoses is preferred (when possible) to recording a list of signs and symptoms. However, if a diagnosis is known and there are other signs or

symptoms that are not generally part of the diagnosis, the diagnosis and each sign or symptom will be recorded separately.

Adverse Events based on examinations and tests

Deterioration as compared to baseline in protocol-mandated laboratory values and vital signs should therefore only be reported as AEs if they fulfill any of the SAE criteria or are the reason for discontinuation of treatment with the investigational product.

If deterioration in a laboratory value/vital sign is associated with clinical signs and symptoms, the sign or symptom will be reported as an AE and the associated laboratory result/vital sign will be considered as additional information. Wherever possible the reporting investigator uses the clinical, rather than the laboratory term (e.g., anemia versus low hemoglobin value). In the absence of clinical signs or symptoms, clinically relevant deteriorations in non-mandated parameters should be reported as AE(s).

Deterioration of a laboratory value, which is unequivocally due to disease progression, should not be reported as an AE/SAE.

Any new or aggravated clinically relevant abnormal medical finding at a physical examination as compared with the baseline assessment will be reported as an AE.

Disease progression

Disease progression can be considered as a worsening of a subject's condition attributable to the disease for which the investigational product is being studied. It may be an increase in the severity of the disease under study and/or increases in the symptoms of the disease. The development of visual loss from diabetic retinopathy, diabetic and other ischemic ulcers, symptomatic hyperglycemia or hypoglycemia should be considered as disease progression and not an AE. Events, which are unequivocally due to disease progression, should not be reported as an AE during the study.

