1.2 Research hypothesis

Both aspirin-ticagrelor and ticagrelor monotherapy will be superior to aspirin monotherapy in the reduction of whole blood viscosity at the end of each 4 week treatment period.

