1.3 Rationale for conducting this study

A previous study comparing 120 patients having intermittent claudication with normal age-matched controls found blood viscosity was significantly higher among claudicants ($p<0.001$) with the greatest difference in blood viscosity observed at lowest shears [3]. At high shear rates, patients with blood viscosity above 4.5 cP had mean claudication distance of 126 meters compared to 289 meters for patients with high-shear viscosity below that threshold. This report suggested the use of the term rheological claudication to describe approximately 25% of moderate to severe claudicants with hyperviscosity of blood having significantly worse prognoses.

In a random sample of 1,581 men and women 55 to 74 years of age with symptomatic or asymptomatic PAD, whole blood viscosity and fibrinogen were independently associated with peripheral arterial narrowing [4]. Plasma viscosity was also associated with claudication. The risk of claudication for patients in the upper quintile of plasma viscosity was 3.4 times greater than the risk for those in the lowest plasma viscosity quintile. The authors implicated blood rheological factors in the pathogenesis of lower limb ischemia in the general population.

The link between blood viscosity and ischemic heart disease events or strokes was reported in a study of a random population of 1,592 adults followed for a mean of 5 years: After adjustment for age and gender, both blood viscosity and hematocrit-corrected blood viscosity were higher in patients who experienced CVD events (myocardial infarction, angina pectoris, coronary revascularization or stroke) than in those who did not. The difference in blood viscosity between the two groups of patients was significant ($p=0.0003$) [5]. A number of outcome studies have demonstrated the risk of major CVD events increased with blood viscosity [6,7]. Stroke patients and those with stroke risk factors were shown to have chronically elevated blood viscosity relative to healthy controls [8].

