A number of observational studies have reported increased blood viscosity in type 2 diabetics compared with nondiabetics. In an early clinical study comparing 16 diabetics with 16 age and gender-matched nondiabetic control subjects, mean blood viscosity at low shear rate was observed to be 26% higher in diabetics ($p<0.001$) [9]. A study of 38 male diabetics with and without retinopathy compared against 38 nondiabetics, matched for age and smoking habit, found low-shear blood viscosity levels were on average 13% higher in diabetics without retinopathy and 30% higher in those with retinopathy relative to control subjects [10]. These differences persisted after adjusting for hematocrit. A separate study of 64 diabetics and 61 matched nondiabetics reported similar results: elevated mean viscosity levels in diabetics compared with control subjects and the highest increases in diabetics with retinopathy or nephropathy [11].

Pharmacological therapies for reducing blood viscosity have been limited to clopidogrel [12], aspirin-dipyridamole [13] and in some studies pentoxifylline [14,15]. A reduction in blood viscosity has not been observed with either cilostazol [15] or ticlopidine [16]. In a double-blind, placebo-controlled study of 30 age and gender-matched patients with subclinical carotid or femoral atherosclerosis, clopidogrel was observed to reduce mean low-shear blood viscosity by 18% from baseline levels 3 weeks after administration (p<0.01) [12].

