1.4 Benefit/risk and ethical assessment

The cross-over study design exposes each randomized group to each of the three treatments, thus reducing treatment bias. Aspirin monotherapy for treatment of PAD is technically an off-label use, however, it remains a Class I recommendation by the ACCF/AHA Task Force on Practice Guidelines when given in daily doses of 75 to 325 mg as a safe and effective antiplatelet therapy to reduce risk of CVD events in those with symptomatic lower extremity PAD [17]. Patients should be counseled on the importance of not taking aspirin outside of the study because doses greater than 100 mg/day can reduce the efficacy of ticagrelor [18]. When possible, if ticagrelor treatment results in bleeding, the bleeding should be managed without stopping therapy as increased risk of CVD events can occur. Also, patients with history of hyperuricemia, gouty arthritis, hepatic impairment, and renal impairment should be monitored closely if taking ticagrelor.

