After 2 weeks run-in treatment with aspirin 81 mg daily, patients will be randomized to one of 3 arms (ticagrelor placebo and aspirin 81 mg (Group A), ticagrelor and aspirin 81 mg (Group B), or ticagrelor monotherapy with aspirin placebo (Group C)) and treated for 4 weeks. At this initial visit and every visit thereafter, laboratory assessments will be performed, including whole blood viscosity, complete blood count (CBC), fibrinogen, globulins, lipid profile, ankle/toe brachial index, and pulse volume recording (PVR). Vital signs will also be assessed at each visit. At the end of 4 weeks treatment, all 3 groups will receive aspirin 81 mg for 2 weeks to reestablish baseline values. After the 2-week washout, the ticagrelor placebo and aspirin 81 mg treatment group (Group A) will be treated with aspirin 81 mg daily and ticagrelor; the aspirin 81 mg daily and ticagrelor treatment group (Group B) will be treated with ticagrelor monotherapy; and, the ticagrelor monotherapy group (Group C) will be treated with ticagrelor placebo and aspirin 81 mg daily for 4 weeks. After the end of 4 weeks treatment, again, all 3 groups will receive aspirin 81 mg for 2 more weeks to re-establish baselines. After this 2-week washout period, the third and final treatment will be for 4 weeks as follows: ticagrelor monotherapy for Group A, ticagrelor placebo and aspirin 81 mg for Group B, and ticagrelor with aspirin 81 mg for Group C. After randomization, the time-window beginning with Visit 1 and for

The 3 treatment groups will receive:

1. Group A: Aspirin 81 mg daily and ticagrelor placebo twice daily
2. Group B: Aspirin 81 mg daily and ticagrelor 90 mg twice daily
3. Group C: Aspirin placebo daily and ticagrelor 90 mg twice daily

Each treatment group will receive all 3 of the above treatments in this cross-over study.

Figure 1. Study Flow Sheet

^a Laboratory Assessments: whole blood viscosity, CBC, fibrinogen, globulins, lipid profile, ankle/toe brachial index, pulse volume recording (PVR).

^b Time Window is ± 7 days.

^c ABI with exercise will be done at screening to identify subjects with claudication symptoms who may have resting ABIs > 0.85 .

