6.2.2 Follow-up procedures

The schedule for follow-up visits is described in Section 3.1. At each follow-up visit, laboratory assessments will be performed, including whole blood viscosity, complete blood count (CBC), fibrinogen, globulins, lipid profile, ankle/toe brachial index, pulse volume recording (PVR) and laser flow Doppler assessment. Some of the laboratory samples will be stored in a -70°C freezer for future assessments and genetic testing. Vital signs, medication adherence, medication safety, and medication efficacy will also be assessed at each visit.

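### The planned outputs would not show whether a modest fall in viscosity on ticagrelor came with a fall in haematocrit, although blood counts are taken at every viscosity visit

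*Combined protocol and SAP*

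**What the plan says.** **AE rule (6.4.3).** "Deterioration as compared to baseline in protocol-mandated laboratory values and vital signs should therefore only be reported as AEs if they fulfill" an SAE criterion or are the reason for discontinuing the investigational product. If there are symptoms, the symptom is the AE and the laboratory value is supporting information. A clinically relevant deterioration without symptoms is reportable only when the parameter is not mandated.

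**What is mandated.** Sections 3.1 and 6.2.2 put the CBC alongside whole blood viscosity at the initial visit and each later one. Section 6.2.2 adds: "Vital signs, medication adherence, medication safety, and medication efficacy will also be assessed at each visit". No output is attached to that assessment.

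**Safety outputs.** Safety variables (11.2) and the safety analysis set (12.1.2) are marked not applicable. Section 2.3 says the study is not designed to compare safety between treatments.

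**Primary endpoint and model.** The hypothesis in 1.2 is that both ticagrelor regimens are "superior to aspirin monotherapy in the reduction of whole blood viscosity at the end of each 4 week treatment period". Sections 12.1 to 12.2 specify a repeated measures ANOVA with treatment, period and sequence effects, two one-tailed contrasts at 0.025, and paired carryover checks of day 1 against weeks 6 and 12. Viscosity is the only dependent variable named.

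**Haematocrit and bleeding elsewhere.** The rationale (1.3) reports that "both blood viscosity and hematocrit-corrected blood viscosity were higher in patients who experienced CVD events" and, for diabetics compared with controls, that "These differences persisted after adjusting for hematocrit". Section 1.4 anticipates bleeding: "When possible, if ticagrelor treatment results in bleeding, the bleeding should be managed without stopping therapy". Section 5.1 bars blood donation and transfusion during the study.

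**The concern.** Keeping mandated laboratory values off the AE form is a common rule. It works when those values are tabulated from the laboratory data, and here no such table is planned. A moderate, symptom-free haemoglobin fall during a ticagrelor period would therefore normally appear neither as an AE nor in a summary. Section 1.4 asks that ticagrelor be continued through bleeding when possible, so the discontinuation route to an AE is less likely to be used.

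The gap bears on efficacy because the endpoint is not corrected for haematocrit. If low-shear viscosity falls with haematocrit, a possible harm (blood loss) and the hoped-for benefit (lower viscosity) move the primary endpoint in the same direction. The authors know that the distinction matters, since 1.3 twice cites findings that allow for haematocrit, but Section 12 does not carry it over. What is at stake is the interpretation of a small significant contrast, which could be presented as a rheological benefit with nothing in the planned results to show what happened to the blood count.

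**Working it through.** **1. Follow one case through the plan.** Take a symptom-free fall of moderate size in a ticagrelor period.
- The CBC is mandated (3.1, 6.2.2), so 6.4.3 allows an AE only through an SAE criterion or discontinuation.
- A dangerous fall could qualify as an important medical event (6.4.2). A moderate one normally would not.
- No safety table exists (11.2, 12.1.2).
- The model (12.1, 12.1.1) has no haematocrit term and no haematocrit output.
- The carryover checks (12.2) compare viscosity. They might respond to a persistent fall but would not identify haematocrit as the cause.

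The value is in the database but in no planned output.

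**2. The plan's sample size (12.3).** Inputs: difference 2.0 cP, SD 2.42 cP, 90% power, type I error 5%. Treating the comparison as two independent groups at one-sided 0.05:

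n per group = 2 × [2.42 × (1.645 + 1.282) / 2.0]² = 25.1, rounded up to 26.

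The plan states 24 per group; power at 24 is 88.8%, so this is close. Also 72 / 0.80 = 90 randomised.

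**3. The smallest significant result.** The contrasts act as paired tests at one-tailed 0.025. With 72 completers:

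SE = 2.42 × √(2(1 − ρ)/72); smallest significant observed difference = 1.994 × SE (t, 71 df).

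The within-patient correlation ρ is assumed, because the documents give none.

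| ρ (assumed) | SE, cP | Smallest significant difference, cP | Share of 9.98 cP |
|---|---|---|---|
| 0.3 | 0.337 | 0.67 | 6.7% |
| 0.5 | 0.285 | 0.57 | 5.7% |
| 0.8 | 0.180 | 0.36 | 3.6% |

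A difference well below the 2.0 cP target can be significant.

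**4. What haematocrit could contribute.** Assume viscosity at 5 s⁻¹ falls by k = 4% (range 2% to 6%) per haematocrit point. The documents give neither the direction nor the size of this effect. From the planning mean of 9.98 cP, a fall of h points lowers viscosity by 9.98 × [1 − (1 − k)^h].
- One point (h = 1): 9.98 × k = 0.40 cP (0.20 to 0.60), or 20% (10% to 30%) of 2.0 cP.
- Mean fall, relative to aspirin, that alone reaches the smallest significant difference: ln(1 − d/9.98)/ln(1 − k). At ρ = 0.5 and k = 4%, d = 0.569 gives 1.4 points. The range is 0.6 (ρ 0.8, k 6%) to 3.5 (ρ 0.3, k 2%).
- Mean fall needed to produce the full 2.0 cP: 5.5 points (3.6 to 11.1).

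**5. Illustration with a minority affected.** Assume further that 2 g/dL equals 6 haematocrit points, that affected patients fall by that amount on ticagrelor and recover, and that none fall on aspirin. Six points are worth 2.17 cP (1.14 to 3.10). If 10% are affected, the mean shift is 0.1 × 2.17 = 0.22 cP. With no other drug effect, the chance of a significant contrast (noncentral t, 71 df) is:

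| Patients affected | Central (ρ 0.5, k 4%) | Range (ρ 0.3, k 2% to ρ 0.8, k 6%) |
|---|---|---|
| 0% | 2.5% | 2.5% |
| 1% | 3.0% | 2.7% to 3.7% |
| 5% | 5.6% | 3.6% to 13% |
| 10% | 11% | 5.2% to 39.5% |

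If falls persist into later aspirin periods, one third to two thirds of the shift remains, and the central figure at 10% drops to about 4% to 7%. These are not error rates for the stated hypothesis, because viscosity has truly fallen in each case.

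**6. A true 2.0 cP effect.** Power with 72 completers exceeds 0.999 for ρ from 0.3 to 0.8, and a haematocrit contribution of the sizes in step 5 would not overturn it.

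**The case against.** The strongest reply is that nothing is lost. Section 6.4.3 governs AE forms and removes no CBC value from the database, so anyone could tabulate haematocrit later. That is right, and it limits the point to the analysis plan. A reader might infer that a viscosity reduction could never be told apart from occult blood loss. The documents do not support that, because counts paired with viscosity will exist for each treatment period.

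Second, the hypothesis concerns whole blood viscosity, and a haematocrit-driven fall is a true fall in it. The protocol claims no mechanism independent of haematocrit, and 2.3 disclaims safety comparison. The first part stands: the primary test is not invalidated. Section 2.3, however, covers comparing safety between treatments and does not explain the primary result.

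Third, the size is nearly all assumption. At the central values, falls of 2 g/dL alone would need about 26% of patients affected (0.57/2.17) to bring the mean shift up to the significance threshold, and the 39.5% figure combines the most favourable slope, correlation and rate. The eligibility criteria exclude known bleeding disorders, recent gastrointestinal bleeding, patients judged at risk of haemorrhage, oral anticoagulation and long-term NSAID use, and each period lasts four weeks. This stands: rates of 5% to 10% are illustrative only.

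Fourth, a lower haematocrit does not show that blood was lost, and an AE threshold of 2 g/dL would miss the small mean shifts that matter for the contrast (one point is about 0.33 g/dL on the assumed conversion). Both stand. The threshold is therefore optional.

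**Conclusion.** The point holds as a gap in the planned outputs. Followed as written, the plan reports nothing that shows whether a modest viscosity reduction on ticagrelor came with a haematocrit fall, or how haemoglobin changed by treatment. It does not make the primary test invalid, and it does not threaten a true 2.0 cP effect.

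The size is unknown. The figures rest on the protocol's mean, SD and sample size together with assumed values for the within-patient correlation, the viscosity change per haematocrit point, the g/dL conversion and the share of patients affected. On those values a mean haematocrit fall of about 0.6 to 3.5 points could alone yield a significant contrast, while the full 2.0 cP would need about 3.6 to 11.1. A reader might also take a haematocrit fall as proof of bleeding; the planned measurements cannot establish that.

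The laboratory parameters table named in the list of tables is not in the text available, so whether it names haematocrit cannot be checked. A list of parameters would not supply an analysis in any case. This is a cheap improvement worth considering before the data are unblinded.

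**What to change.** **12.1.2:** replace the not-applicable entry with a safety set of all patients given at least one dose of randomised treatment. Summarise AEs, and haemoglobin and haematocrit change over each treatment period, by treatment, descriptively and without tests. Show AEs that start in a washout under the preceding treatment.

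**12.1.1:** report mean haematocrit change by treatment beside each primary contrast. Repeat each contrast with same-visit haematocrit as a covariate, labelled supportive: haematocrit is measured after treatment, so the adjusted result helps to explain the primary contrast and does not replace it.

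**6.4.3 (optional):** the investigators may set a haemoglobin fall, for example 2 g/dL from the start of the current period, that is reported as an AE with or without symptoms. This would help safety recording but is not needed to interpret the primary contrast.

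**Cost:** one descriptive table and one supportive model, with no new blood draws; the optional threshold would add a few AE forms. The main risk is that the adjusted contrast is misread as the main result, so its status must be stated wherever it is reported.

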6.4.4 Reporting of serious adverse events

Investigators and other site personnel must inform the FDA, via a MedWatch/AdEERs form, of any serious or unexpected adverse events that occur in accordance with the reporting obligations of 21 CFR 312.32, and will concurrently forward all such reports to AZ. A copy of the MedWatch/AdEERs report must be faxed to AstraZeneca at the time the event is reported to the FDA. It is the responsibility of the investigator to compile all necessary information and ensure that the FDA receives a report according to the FDA reporting requirement timelines and to ensure that these reports are also submitted to AstraZeneca at the same time.

When reporting to AstraZeneca, a cover page should accompany the MedWatch/AdEERs form indicating the following:

- Investigator Sponsored Study (ISS)

- The investigator IND number assigned by the FDA
- The investigator's name and address
- The trial name/title and AstraZeneca ISS reference number

Investigative site must also indicate, either in the SAE report or the cover page, the causality of events in relation to all study medications and if the SAE is related to disease progression, as determined by the principal investigator.

Send SAE report and accompanying cover page by way of fax to AstraZeneca's designated fax line: [name]

Serious adverse events that do not require expedited reporting to the FDA need to be reported to AstraZeneca preferably using the MedDRA coding language for serious adverse events.

In the case of blinded trials, AstraZeneca will request that the Sponsor either provide a copy of the randomization code/ code break information or unblind those SAEs which require expedited reporting.

All SAEs have to be reported to AstraZeneca, whether or not considered causally related to the investigational product. All SAEs will be documented. The investigator is responsible for informing the IRB and/or the Regulatory Authority of the SAE as per local requirements.

We will submit SAE reports to AstraZeneca using the MedDRA coding language.

6.4.5 **Laboratory safety assessment**

All laboratory equipment and devices will be regularly evaluated by the site and/or outside auditors for Good Clinical Practice and overall laboratory safety.

For the purpose of ensuring compliance with Good Clinical Practice and regulatory agency guidelines, it may be necessary for the Sponsor or a regulatory agency to conduct a site audit or an inspection.

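### Section 6.4.3 classes four kinds of diabetic and ischemic event as disease progression rather than adverse events, with no exception for serious cases, in conflict with Sections 6.4.1 and 6.4.4 and with other rules in 6.4.3

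*Combined protocol and SAP*

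**What the plan says.** Section 6.4.3 of the combined protocol and SAP ends with a paragraph on disease progression. It defines progression as a worsening put down to the disease under study, then gives a list. The list opens with "The development of visual loss from diabetic retinopathy" and continues: "diabetic and other ischemic ulcers, symptomatic hyperglycemia or hypoglycemia should be considered as disease progression and not an AE". The paragraph closes with a general rule: "Events, which are unequivocally due to disease progression, should not be reported as an AE during the study". It does not mention seriousness.

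Other text bears on the same events:

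- **6.4.1** counts as an AE "the deterioration of a pre-existing medical condition following or during exposure to a pharmaceutical product, whether or not considered causally related to the product". It adds that the term covers serious and non-serious events alike.
- **6.4.2** builds the SAE on the AE: "A serious adverse event is an AE occurring during any study phase" and meeting at least one criterion. One criterion reads "Requires in-patient hospitalization or prolongation of existing hospitalization"; another is lasting or significant disability.
- **6.4.3, examinations and tests**, makes an AE of any clinically relevant examination finding that is new or worse than at baseline. Where a worsening laboratory value comes with symptoms, the symptom is an AE.
- **6.4.4** states: "All SAEs have to be reported to AstraZeneca, whether or not considered causally related to the investigational product". The site must also indicate "if the SAE is related to disease progression, as determined by the principal investigator".

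**The concern.** The listed events are foreseeable in people with type 2 diabetes and symptomatic PAD, and some will be serious. If they are taken out of the AE category before seriousness is considered, they may never enter the SAE pathway.

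Much depends on that pathway. SAE status leads to reporting under 6.4.4, to follow-up until recovery or stabilization under 6.4.3, and to decoding of treatment under 5.4.2; 5.9 gives an SAE as its example of harm requiring withdrawal. Little stands behind it: safety variables (11.2) and the safety analysis set (12.1.2) are marked not applicable, and 12.4 plans no data monitoring committee unless an IRB at a clinical site asks for one. The documents describe no other recording route for the listed events. Ischemic ulcers are also limb events, in a trial with peripheral arterial blood flow as a secondary objective (2.2).

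The second risk is inconsistency. Section 6.5 refers to three sites. A site that applies the examination rule and a site that applies the progression list will record the same ulcer differently, and both can point to the protocol.

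**Working it through.** No arithmetic applies. The check is to follow one event through each rule.

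**Step 1: does the list depend on case-by-case judgment?** No. The closing sentence of the progression paragraph is limited to events unequivocally due to progression, which calls for a judgment. The sentence before it classes the named events outright.

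**Step 2: can a listed event still be an SAE?** By 6.4.2 an SAE is an AE plus a seriousness criterion. By the list, the event is not an AE. The criterion is therefore never reached, and the duty in 6.4.4 to report all SAEs has nothing to act on.

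**Step 3: is there a seriousness exception elsewhere in 6.4.3?** There is one. Deterioration in protocol-mandated laboratory values and vital signs becomes an AE if it meets an SAE criterion (or leads to stopping the product). It does not extend to the progression list. A nearby sentence takes laboratory deterioration that is clearly due to progression out of both AE and SAE reporting.

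**Step 4: set the outcomes side by side.**

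| Event | Progression list with 6.4.2 | Other rules |
|---|---|---|
| New ischemic ulcer found on examination, no admission | Not an AE | AE (6.4.3, examination rule) |
| Ischemic ulcer with hospital admission | Not an AE, so not an SAE | SAE (6.4.1 and 6.4.2); reported with progression statement (6.4.4) |
| Symptomatic hypo- or hyperglycemia with abnormal glucose | Not an AE | Symptom is an AE (6.4.3, symptom rule); SAE if admitted |
| Visual loss from diabetic retinopathy, disabling | Not an AE, so not an SAE | SAE (6.4.1 and the disability criterion in 6.4.2) |

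Every row gives two answers.

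**Step 5: how direct is each conflict?** The conflict with 6.4.1 and with the examination and symptom rules is direct, since the same event is and is not an AE. The conflict with 6.4.4 is one of evident intent. An event that is not an AE cannot literally breach a rule about all SAEs, but the required progression statement shows that 6.4.4 expects progression-related SAEs to arrive. Under the strict reading that statement would be left only for unlisted events whose link to progression is in doubt.

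**The case against.** The strongest reply is that the sections can be harmonised. The progression paragraph says only that the events are not AEs, while the laboratory sentence in the same section names both AEs and SAEs, so the authors mentioned SAEs when they meant them. Section 6.4.4 is the specific SAE section and presupposes that progression-related SAEs are reported. On this reading, progression is kept off the routine AE log and serious cases still go through 6.4.4.

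That reading is possible, and it is probably what was intended. It is not what 6.4.2 and the progression paragraph say together, and a site has no text telling it to read them that way. What stands of the objection is that loss of serious events is a risk, not a certainty. A reader might infer that a site following the protocol would necessarily leave out an admission for hypoglycemia. The documents do not support that, because the same site is also bound by 6.4.4 and by the examination and symptom rules.

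A reader might also argue that retinopathy and glycemic events cannot be progression because the disease under study is PAD alone. That is contestable. Type 2 diabetes is an entry criterion (4.1), 3.1 describes the population as diabetic patients with PAD, and 1.3 links viscosity to diabetic retinopathy. Hypoglycemia fits poorly even on the wider reading, but the point does not need this argument.

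Other monitoring exists: 6.2.2 has vital signs, blood counts and medication safety assessed at each follow-up visit, and 5.9 requires withdrawal if the study appears harmful. These lessen the consequence without settling how a listed event is recorded.

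**Conclusion.** The point holds as a contradiction in the reporting rules under which serious events may go unrecorded and unreported. It rests on two textual facts: the progression list has no seriousness exception, and an SAE must first be an AE. That serious cases are covered by the list is an inference from these, not a statement in the protocol.

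The reach is limited. Four kinds of event are named: visual loss from diabetic retinopathy, diabetic and other ischemic ulcers, symptomatic hyperglycemia and symptomatic hypoglycemia. Visual loss from other causes is not excluded. The documents give no incidence for any of them, so the number of events at risk cannot be estimated. The 90 patients in 12.3 are those to be randomized, which happens after the run-in, so 90 should not be read as the number exposed to the rule during run-in.

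The effect is on safety capture and on consistency between sites. The viscosity comparisons are untouched, and 2.3 says the study is not designed to compare safety between treatments. For that reason the point does not support asking for these events to be listed by treatment period. It should be corrected, but it does not threaten the primary analysis.

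**What to change.** Reconcile 6.4.1 to 6.4.4 by adding to the progression paragraph of 6.4.3 text to this effect:

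*The disease-progression exception applies only to non-serious events. Any listed event that meets a criterion in Section 6.4.2 is recorded and reported as an SAE under Section 6.4.4, with the statement on relation to disease progression.*

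Two consequential edits belong with it. The laboratory sentence in 6.4.3 that removes progression from both AE and SAE reporting should be aligned with the new text. One further sentence should say whether the progression exception or the examination and symptom rules prevail for a non-serious listed event, so that all sites do the same.

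Cost: a written amendment signed by the principal investigator and the sponsor, with ethics approval (8.4); documented training of site staff (9.1); and a few more SAE reports. The progression statement is already required, so it adds no new item to the SAE report.
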